8.2 Administration of Study Drug

Patients will be dosed with 120 µg/kg/day or 40 µg/kg/day⁴ for 72 weeks or 40 µg/kg/day for the first 12 weeks followed by 120 µg/kg/day for the remaining 60 weeks⁴. Patients not tolerating the 120 µg/kg/day dose after a minimum of 1 week, for reasons other than new liver findings and severe diarrhea, will have the option to down-titrate to a lower dose (40 µg/kg/day). They should return to the higher dose as soon as deemed appropriate by the investigator. More than one upward dose titration (from 40 µg/kg/day directly to 120 µg/kg/day) for the same event is not recommended. If, in the opinion of the investigator, a dose titration should be considered prior to the 1 week minimum, the investigator should consult with the Medical Monitor or designee. Any dose titration should be done in consultation with the sponsor Medical Monitor or designee.

Study drug will be dispensed to the patient at defined intervals from Visit 1 through Visit 9, together with instructions on how to store and take the drug. Study drug administration data, including whether each patient took each dose or partial doses of study drug, whether there were any delayed or missed doses, and whether the capsule was opened or swallowed whole, will be documented through the diaries and transferred to the study database.

⁴ As of Protocol Amendment 6 patients entering Cohort 2 will start treatment at 40 µg/kg/day with the possibility to dose escalate to 120 µg/kg/day after 12 weeks if there is no improvement in pruritus based on investigator judgment.

Patients participating in the optional extension period will continue at the same dose as at the end of the 72-week treatment period (120 µg/kg/day or 40 µg/kg/day). Patients not tolerating the 120 µg/kg/day dose at any time throughout the extension period will have the option to down-titrate to a lower dose (40 µg/kg/day) following consultation with the sponsor Medical Monitor or designee. Patients should return to the higher dose as soon as deemed appropriate by the investigator. More than one upward dose titration (from 40 µg/kg/day directly to 120 µg/kg/day) for the same event is not recommended.

A4250 should be taken in the morning together with food. On clinic visits days when laboratory assessments are conducted (Visits 1 to 10; or Visits 1 to XX for those participating in the optional extension period), study drug should be taken after the visit. Patients should not crush or chew the capsule(s). When swallowing the capsule intact, the patient should administer the dose with a glass of water.

If the study medicine needs to be mixed in a small amount of food because the patient is unable to swallow the capsule intact, the capsule can be twisted open and the contents sprinkled and mixed in a small amount (one or two tablespoons (15 to 30 mL)) of room-temperature yogurt, apple sauce, oatmeal, or fruit purée. If the patient has not yet been weaned onto solid foods, the capsule contents can be sprinkled into a small amount (a few milliliters) of water, baby formula or breast milk and administered with an oral dosing pipette. Please see Pharmacy manual for detailed instructions.

If a patient's weight changes at any time during the study, dose adjustment will be required. The number of capsules provided to the patient should be based on the body weight thresholds identified in [Table 3](#).

Table 3 Dosing and Capsule Strength

Body Weight (kg)	Capsule Size	Number of Capsules per Day ^{a,b}	Capsule Strength, Low Dose ^a (µg)	Total Dose (µg) ^a	Capsule Strength, High Dose ^b (µg)	Total Dose (µg) ^b
5 to <7.5	0	1	200	200	600	600
7.5 to <12.5	0	2	200	400	600	1200
12.5 to <17.5	0	3	200	600	600	1800
17.5 to <19.5	0	4	200	800	600	2400
19.5 to <25.5	3	2	400	800	1200	2400
25.5 to <35.5	3	3	400	1200	1200	3600
35.5 to <45.5	3	4	400	1600	1200	4800
45.5 to 55.5	3	5	400	2000	1200	6000
>55.5	3	6	400	2400	1200	7200

a Low dose: 40 µg/kg/day

b High dose: 120 µg/kg/day

8.3 Study Drug Packaging and Labelling

8.3.1 Packaging and Labelling

The capsules will be packed in high-density polyethylene containers, with childproof polypropylene caps. Study drug capsules containing A4250 in the strength specified in the table above will be manufactured.

Packaging and labelling will be prepared to comply with applicable regulatory requirements.

8.3.2 Storage

Treatment packs containing A4250 capsules should be stored and dispensed in accordance with regulations in their original containers. The storage facility at the investigative site should be locked and storage should be between 15°C and 25°C.

Patients/caregivers should be informed of appropriate storage conditions (i.e., room temperature, between 15°C and 25°C).

Any deviations from the recommended storage conditions should be immediately reported to Albireo and the study drug should not be used until authorization has been given by Albireo.

8.3.3 Blinding and Randomization of Study Drug

Not applicable.

8.4 Procedure for Breaking the Randomization Code

Not applicable.

8.5 Patient Compliance

The study nurse will monitor eDiary compliance by routine review of the CRF Health website. Patient/caregivers will be instructed to fill in the eDiary every morning and evening for the first 24 weeks and the last 21 days before all the remaining visits to the clinic. There will be no interruption between Visits 11 and 12. Patients participating in the optional extension period will stop eDiary entries at Visit 11. If both diary entries on a day are missing during this time, the study nurse will call the caregiver/patient to remind them to complete all scheduled entries. Any non-compliance will be documented and explained in the source documents.

Study drug compliance will be assessed by review of returned unused medication and by counting returned capsules at Visits 2 through 11 or Visits 2 through XX if participating in the optional extension phase, inclusive. Study drug compliance will be calculated for each patient and listed.

Treatment Compliance = $100 \times ((\text{Number of study drug dispensed} - \text{number of study drug returned}) / \text{number of study drug that should be taken})$

Treatment compliance between 80% and 120% will be acceptable.

8.6 Patient Identification

After written informed consent is obtained from an eligible patient, an 8-digit patient identification number will be assigned. The first 2 digits will denote the country, followed by a 3-digit site number and a 3-digit patient sequence number. This number will be captured by the IWRS, when the patient first enters the system in A4250-008. Cohort 1 patients will be assigned the same patient number as used in the A4250-005 study, while Cohort 2 patients will be assigned a new unique patient number.

8.7 Study Drug Accountability

Records shall be maintained of the delivery of study treatment to the study site(s), the inventory at the study site(s), the use of each patient and the return to Albireo.

These records shall include dates, quantities, batch numbers, expiry dates and the unique code numbers assigned to the study drug and to the study patients.

The investigator will be responsible for ensuring that the records adequately document that the patients were provided the quantities specified in the protocol and that all study drug received from Albireo is reconciled.

8.8 Concomitant Therapy and Prohibited Medications

For Cohort 1 patients, the investigator will note all ongoing medication in the eCRF at Visit 1. For Cohort 2 patients, the investigator will note all ongoing medication and any medication recently stopped (within 1 month prior to Visit S-1) in the eCRF at Visit S-1. At Visits 2 to 12, (and S-2 for Cohort 2) and visits in the optional extension period, all changes in medication (stopping or starting new medication or changes in dose) will be recorded in the eCRF. All medication (prescribed or over the counter) for pruritus, sleep, and vitamin supplementation will be recorded.

All medications still being taken by a patient on or after first intake of study drug and which continue to be taken during the study are regarded as concomitant medication.

The protocol allows for patients to be vaccinated against COVID-19 while in the study, based on the treating physician's clinical assessment of the risks and benefits of study participation. Therefore, the COVID-19 vaccine can be administered as a concomitant medication. The date of COVID-19 vaccination must be recorded in the clinical database if administered during study participation.

Concomitant medication guidelines are listed in [Appendix 1](#).

9 ASSESSMENT OF EFFICACY

9.1 Efficacy Endpoints

9.1.1 Primary Efficacy Endpoints

The primary efficacy endpoints are:

EU and rest of world: Change from baseline in serum bile acids after 72 weeks of treatment.

US: Proportion of positive pruritus assessments at the patient level over the 72-week treatment period using the Albireo ObsRO instrument.

9.1.2 Secondary Efficacy Endpoints

EU and rest of world: Proportion of positive pruritus assessments at the patient level over the 72-week treatment period using the Albireo ObsRO instrument.

US: Change from baseline in serum bile acids after 72 weeks of treatment.

All Regions:

- Change from baseline in serum bile acids at Weeks 4, 12, 22, 24, 36, 46, 48, 60, 70, 72, and 76
- Proportion of individual assessments meeting the definition of a positive pruritus assessment at the patient level using the Albireo ObsRO instrument from Weeks 0-4, Weeks 0-12, Weeks 0-22, Weeks 0-24, Weeks 0-36, Weeks 0-46, Weeks 0-48, Weeks 0-60, and Weeks 0-70, respectively, or the proportion of positive pruritus assessments at each 4-week interval between Visit 1/Screening and Visit 5/Week 24, then by each visit between Visit 5/Week 24 to Visit 12/Week 76
- Proportion of individual AM assessments meeting the definition of a positive pruritus assessment at the patient level using the Albireo ObsRO instrument from Weeks 0-4, Weeks 0-12, Weeks 0-22, Weeks 0-24, Weeks 0-36, Weeks 0-46, Weeks 0-48, Weeks 0-60, Weeks 0-70, and Weeks 0-72, respectively, or the proportion of positive pruritus assessments at each 4-week interval between Visit 1/Screening and Visit 5/Week 24, then by each visit between Visit 5/Week 24 to Visit 12/Week 76
- Proportion of individual PM assessments meeting the definition of a positive pruritus assessment at the patient level using the Albireo ObsRO instrument from Weeks 0-4, Weeks 0-12, Weeks 0-22, Weeks 0-24, Weeks 0-36, Weeks 0-46, Weeks 0-48, Weeks 0-60, Weeks 0-70, and Weeks 0-72, respectively, or the proportion of positive pruritus assessments at each 4-week interval between Visit 1/Screening and Visit 5/Week 24, then by each visit between Visit 5/Week 24 to Visit 12/Week 76
- All-cause mortality, number of patients undergoing biliary diversion surgery or liver transplantation. These parameters will be evaluated separately and together at weeks 24, 48, and 72

- Change in growth from baseline to Weeks 24, 48, and 72 after initiation of A4250 treatment, defined as the linear growth deficit (height/length for age, weight for age, mid-arm circumference, and body mass index [BMI]) compared to the standard growth curve (Z-score, standard deviation [SD] from P50)
- Change in AST to platelet ratio index (APRI) score and Fib-4 score from baseline to Week 72
- Change in pediatric end-stage liver disease (PELD)/model for end-stage liver disease (MELD) score from baseline to Week 72
- Change in use of antipruritic medication at Weeks 24, 48, and 72

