9.2.7 PELD/MELD Score

The PELD score will be calculated for children up to 12 years of age. For patients 13 years or older, the MELD score will be calculated.

PELD Score = $4.80 * \ln(\text{total bilirubin}) + 18.57 * \ln(\text{INR}) - 6.87 * \ln(\text{albumin}) + 4.36$ (if patient <1 year: scores for patients listed for liver transplantation before the patient's first birthday continue to include the value assigned for age (<1 year) until the patient reaches the age of 24 months) + 6.67 (if patient has growth failure [<-2 SD])

Laboratory values less than 1.0 will be set to 1.0 for the calculation of the PELD score.

MELD Score = $9.57 * \ln(\text{creatinine}) + 3.78 * \ln(\text{total bilirubin}) + 11.2 * \ln(\text{INR}) + 6.43$

Laboratory values less than 1.0 will be set to 1.0 and serum creatinine values greater than 4.0 mg/dL (equivalent to 353.6 $\mu\text{mol/L}$) will be set to 4.0 for calculation of the MELD score.

If a patient goes from 11 years of age to 12 between the beginning and end of study, both PELD and MELD scores will be calculated at the first visit after the 12th birthday and move to MELD score. The results should be displayed in one summary table.

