9.2.9 Markers of Fibrosis

APRI score and Fib-4 score will be calculated at Visits 1, 3, 5, 8, and 11.

APRI = $[(\text{AST in U/L}) / (\text{AST upper limit of normal [ULN] in U/L})] \times 100 / (\text{Platelets in } 10^9/\text{L})$

Fibrosis 4 Score = $(\text{Age} * \text{AST in U/L}) / (\text{Platelets in } 10^9/\text{L} * \sqrt{(\text{ALT in U/L})})$

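### PELD-to-MELD switch age is stated two ways, switchers have no same-scale baseline, and age terms move PELD and, if age at visit is used, Fib-4

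*Protocol*

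**What the plan says.** Section 9.1.2 lists two secondary endpoints of interest: "Change in AST to platelet ratio index (APRI) score and Fib-4 score from baseline to Week 72" and "Change in pediatric end-stage liver disease (PELD)/model for end-stage liver disease (MELD) score from baseline to Week 72". Section 11.2.2.6 has continuous secondary variables described as actual values and as change from baseline.

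Section 9.2.7 gives the scoring rules; its text appears twice in the document, identically.

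- PELD is for children up to 12 years. Then: "For patients 13 years or older, the MELD score will be calculated".
- For a patient who goes from 11 to 12 during the study, "both PELD and MELD scores will be calculated at the first visit after the 12th birthday and move to MELD score".
- On presentation: "The results should be displayed in one summary table".
- PELD carries 4.36 points for age under 1 year. The points are kept to 24 months only for patients listed for transplantation before their first birthday. It also carries 6.67 points for growth failure. MELD has neither term and no albumin term.

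Section 9.2.9 defines Fib-4 with age as a multiplier and says "APRI score and Fib-4 score will be calculated at Visits 1, 3, 5, 8, and 11". It does not say whether age is taken at the visit or at baseline.

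**The concern.** A 12-year-old is scored by PELD under the first rule and by MELD under the second. Reading the first rule as ending at the 12th birthday does not help: 12-year-olds would then have no score under it, because MELD starts at 13. A patient passing from 12 to 13 has no transition rule at all.

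The endpoint is a change from baseline. A switcher starts on PELD and ends on MELD, and the two scores are on different scales. The only visit at which both are required is the first one after the birthday, so no MELD baseline and no Week 72 PELD is specified.

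Age also enters PELD directly for infants and multiplies Fib-4. The study has no concurrent control to absorb such shifts. At stake is whether the reported changes in these liver scores describe the liver or the calendar.

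**Working it through.** The protocol states no expected change for these scores, so there is no figure of its own to reproduce. I evaluated its formulas at the start and end of treatment with laboratory values held constant.

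**Time on study.** Table 1 has dosing from Day 1 through Day 504: 504/365.25 = 1.38 years, or 16.6 months.

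**Who can switch.** If the switch is at the 12th birthday, patients aged from 12 − 1.38 = 10.62 years to under 12 at baseline cross during treatment. If it is at 13, the window is 11.62 to under 13.

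**Size of the switch.** Subtracting the Section 9.2.7 formulas, with creatinine at or below 1 (so its logarithm is 0) and bilirubin at or above 1:

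MELD − PELD = 6.43 − 1.02 ln(bilirubin) − 7.37 ln(INR) + 6.87 ln(albumin) − 6.67 (only if growth failure)

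The protocol gives no patient laboratory values and no units for bilirubin or albumin. The inputs below (mg/dL and g/dL) are my assumptions.

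| Bilirubin, INR, albumin | PELD | MELD | Jump, no growth failure | Jump, growth failure |
|---|---|---|---|---|
| 1, 1.0, 4.0 | −9.52 | 6.43 | +15.95 | +9.28 |
| 3, 1.2, 3.5 | 0.05 | 12.62 | +12.57 | +5.90 |
| 10, 1.4, 3.0 | 9.75 | 18.90 | +9.15 | +2.48 |

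The PELD column is without growth failure. The last column is the one before it minus 6.67.

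**Infants on PELD.** Cohort 2 admits any age at 5 kg or more (Section 7.2.1), and Section 9.2.1 provides for infants under 12 months. Anyone under 1 year at baseline passes the first birthday within 16.6 months. If not listed for transplant by then, the patient loses 4.36 points. Above the 1.0 floor for laboratory values, this equals a fall in bilirubin to exp(−4.36/4.80) = 0.40 of its value, a 60% fall. A patient listed before the first birthday keeps the term to 24 months, and so loses it by Week 72 if aged about 24 − 16.6 = 7.4 months or more at baseline.

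**Fib-4, if age at visit is used.** With AST, ALT and platelets unchanged:

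change = (age + 1.38 − age) × AST/(platelets × √ALT) = 1.38 × AST/(platelets × √ALT)

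Baseline age cancels. With assumed AST = ALT = 100 U/L and platelets 300: 1.38 × 100/(300 × 10) = +0.046. The drift is always upward, towards apparent worsening. The APRI formula has no age term.

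**Cohort mean.** No age distribution is given. As an assumed range, 1 to 10 infants among 60 patients would move mean PELD by −4.36/60 = −0.07 to −43.6/60 = −0.73. One to 10 switchers among 60, each at +15.95, would move a pooled mean by +0.27 to +2.66, and by less at the smaller jumps.

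**The case against.** The best defence is that much of this is derivation detail that a SAP, not at hand here, may settle: which age enters Fib-4, and which baseline is paired with a switcher's Week 72 score. No sentence orders a PELD value to be subtracted from a MELD value. The study has no formal testing, actual visit values are shown too, and bilirubin, INR, albumin, liver enzymes and platelets are reported in their own right. Holding age fixed also yields a modified score rather than the defined one.

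Part of this stands, and it limits what can be claimed. A reader might infer any of the following, and the documents do not support them:

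- **That Fib-4 is inflated most in the youngest.** In percentage terms the rise is 138% at age 1 and 14% at age 10, but the endpoint is change in score, not percent change. The absolute drift is the same at every age.
- **That the direction of the Fib-4 drift depends on the age mix.** It is always upward, so it cannot create a false benefit. Only PELD/MELD can move either way.
- **That Fib-4 certainly uses age at visit.** Calculation at five visits makes this the natural reading, but the text does not say so.
- **That one summary table means pooled scales.** It could hold separate rows, although that would not supply the missing same-scale baseline.

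The defence does not reach the conflicting switch ages, which the protocol itself must reconcile. Nor does it reach the PELD age term or the move to MELD, which the protocol fixes alongside a change-from-baseline endpoint.

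**Conclusion.** The point holds in this form. The switch age is contradictory as written, and switchers have no same-scale pair of scores for the change to Week 72. On unchanged laboratory values the switch is worth about +9 to +16 points without growth failure and about +2.5 to +9 with it, under the assumed bilirubin 1 to 10 mg/dL, INR 1.0 to 1.4, albumin 4 to 3 g/dL and creatinine at or below 1. The loss of 4.36 PELD points in unlisted infants follows from the stated formula without assumption. The Fib-4 drift, about +0.05 on assumed values, is conditional on age at visit being used.

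The PELD artefact is confined to infants (and listed patients passing 24 months), and the switch artefact to those crossing 12 or 13. Their effect on the cohort mean cannot be computed from the document. These are descriptive secondary endpoints, so this is a matter of interpretation that should be corrected; the primary endpoints and stated power are not affected.

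**What to change.** - State one switch age in Section 9.2.7, wherever its text appears, so that the general rule and the transition rule agree.
- Compute each patient's change from baseline on a single score at both baseline and Week 72, PELD or MELD according to age at Visit 1. Hold the under-1-year term at its baseline status.
- Summarise PELD and MELD changes in separate rows.
- Compute change in Fib-4 with age held at its baseline value.
- List the scores as defined in the protocol at each visit alongside.

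With unchanged laboratory values and growth status, every one of these changes is then exactly zero. The cost is wording and programming; the inputs are those the two scores already use. The one small downside is the extra listing, needed because the change is no longer the difference between two as-defined visit scores.

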9.1.3 Exploratory Efficacy Endpoints

All Exploratory Endpoints will be evaluated at Weeks 24, 48, and 72 unless otherwise noted. Baseline is calculated prior to initiation of A4250 treatment. Exploratory endpoints include:

- Change in serum ALT, GGT, and total bilirubin concentration from baseline to Week 72
- Proportion of individual assessments meeting the definition of a positive pruritus assessment at the patient level over the 72-week Treatment Period. A positive pruritus assessment includes an itch score ≤ 1 , or at least a one-point drop from baseline based on the Albireo PRO instrument; only patients ≥ 8 years of age will complete the Albireo PRO instrument
- Change from baseline over the 72-week treatment period in sleep parameters measured with the Albireo PRO and ObsRO instruments
- Change from baseline in INR, albumin, liver enzymes, leukocytes, and platelets
- Change from baseline measures of bile acid synthesis (autotaxin, p-C4)
- Assessment of Global Symptom Relief at Weeks 4, 12, 24, 48, and 72 as measured by patient, caregiver, and clinician PGIC items
- Change from baseline by each 4-week interval between Visit 1/Screening and Visit 5/Week 24, then by each visit between Visit 5/Week 24 to Visit 12/Week 76 in patient-reported and observer-reported night time itching and scratching severity scores, respectively
- Change from baseline by each 4-week interval between Visit 1/Screening and Visit 5/Week 24, then by each visit between Visit 5/Week 24 to Visit 12/Week 76 in patient-reported and observer-reported morning time itching and scratching severity scores, respectively
- Change from baseline by each 4-week interval between Visit 1/Screening and Visit 5/Week 24, then by each visit between Visit 5/Week 24 to Visit 12/Week 76 in pooled pruritus score including observer-reported scratching for patients < 8 years of age and patient-reported itch severity for patients ≥ 8 years of age

- Change from baseline by each 4-week interval between Visit 1/Screening and Visit 5/Week 24, then by each visit between Visit 5/Week 24 to Visit 12/Week 76 in additional patient-reported and observer-reported sleep parameters (e.g., tiredness, number of awakenings)
- Change from baseline in PedsQL questionnaire
- Change from baseline in stage of liver fibrosis as assessed by Fibroscan® (where available)
- Change from baseline in stage of liver fibrosis as assessed by post-treatment biopsy (when available)

9.2 Efficacy Assessments

9.2.1 Serum Bile Acids

Blood samples for analysis of fasting serum bile acids will be drawn at all study visits from Visit 1 (Visit S-1 for Cohort 2) through Visit 12. Fasting serum bile acids will also be drawn at all visits during the optional extension period. Patients will fast (only water intake is permissible) for at least 4 hours prior to the collection of samples for serum bile acids. Exceptions can be made for infants, less than 12 months of age, if unable to fast for the full 4 hours. For any visit at which a bile acid sample result is unreportable, an additional unscheduled visit for a repeat sample collection may be scheduled. Samples will be handled and transported to a central laboratory per instructions in the laboratory manual.

